2. SYNOPSIS

2.1 Study objective

We designed this study to assess the long-term outcome after implantation of the supraciliary CyPass microstent beyond two years. The long-term results are of considerable importance for the evaluation and positioning of the CyPass stent procedure in the surgical glaucoma treatment armamentarium. We will collect data of a follow-up period of an average of 5 years.

The main research outcome is the determination of the efficacy of CyPass microstent implantation in reducing the intraocular pressure, the number of necessary antiglaucomatous medications and the progression of glaucoma in terms of visual field worsening and progression of glaucomatous optic disc changes.

Another main outcome is the safety of the procedure based on the intraoperative and postoperative complications.

Secondary outcomes include the development of the stent-associated blebs, the long-term success rate of the CyPass stent, and the clinical identification of stent failures.

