2.4 Study investigation plan

The pre- and intraoperative data, the data of the routine follow-up after 3 and 6 months postoperatively, as well as data of unscheduled examinations are taken retrospectively from the patient files.

- Collection of preoperative findings from the medical record:
 - i. Patient name, date of birth, gender, operated eye and surgery date
 - ii. General diseases and medications
 - iii. Eye diseases and already performed eye operations, if any
 - iv. Best corrected visual acuity
 - v. Topical and systemic glaucoma therapy and duration of glaucoma therapy
 - vi. Time of diagnosis of glaucoma, if available
 - vii. Intraocular pressure using Goldmann tonometer and time of measurement
 - viii. Central corneal thickness and pachymetric correction factor measured with the ultrasonic pachymeter or with Visante-OCT.
 - ix. Classification of the chamber angle width according to Shaffer classification
 - x. The lens condition or existing opacities of the natural lens or presence of an implanted intraocular lens at the time of surgery
 - xi. Visual field using Humphrey perimeter or TAP (Tuebinger automatic perimeter)
 - xii. Optic nerve configuration measured with the HRT-II (Heidelberg Retina Tomograph II)
 - xiii. Retinal nerve fiber layer thickness measured with Stratus OCT
- Collection of intraoperative characteristics or complications from the surgical report

Protocol Version II 5-year CyPass results

- Collection of available postoperative findings and complications
- A written or telephone invitation of the patients to a postoperative examination in the Department of Ophthalmology Neubrandenburg to collect the current, long-term postoperative findings
- The following examinations are performed during the study visit 5 years postoperatively:
 - i. Ophthalmic history
 - ii. Best corrected visual acuity
 - iii. Topical and possibly systemic glaucoma therapy
 - iv. Intraocular pressure using Goldmann tonometer
 - v. Central corneal thickness and the pachymetric correction factor measured with the ultrasonic pachymeter or with the Visante-OCT
 - vi. Visual field using Humphrey perimeter
 - vii. Gonioscopic findings
 - viii. The lens condition or opacities of the natural lens or of the implanted intraocular lens
 - ix. Optic nerve configuration measured with the HRT-II (Heidelberg Retina Tomograph II)
 - x. Nerve fiber thickness measured with Stratus OCT

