2.6 Success of the treatment

We use two classifications to define treatment success:

- The first classification: dividing patients into 2 groups according to the need for postoperative glaucomatous medication: with and without medication. Then we divide each group into 4 subgroups according to the postoperative intraocular pressure achieved: patients with $IOP > 21\text{mmHg}$, patients with $IOP \leq 21\text{mmHg}$ and $> 18\text{mmHg}$, patients with $IOP \leq 18\text{mmHg}$ and $> 15\text{mmHg}$, and patients with $IOP \leq 15\text{mmHg}$.
- The second classification: definition of the treatment success according to the criteria of WGA (World Glaucoma Association) [4]. Complete success is achieved if the target IOP is reached without additional medication. Achieving the target pressure with additional local therapy is rated as qualified success. The loss of visual acuity to 'nulla lux' because of glaucoma progression, the need for systemic therapy with CAI (carbonic anhydrase inhibitor) to reduce pressure or the need for second glaucoma surgery are classified as complete failures.

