4.5 Postoperative data collection

We collect the following data prospectively (at the five-year follow-up visit):

- i. *Intermediate history:* First, asking the patients about the postoperative course and the regular check-ups at the registered ophthalmologist. If available, taking the intermediate eye pressure values and the course of the topical therapy, which may have been documented by the Glaucoma pass. Documentation of events such as bleeding or acute IOP-increase. Also documentation of intermediate treatments with date, if any, such as laser treatments.

ii. *Intraocular pressure:* Measuring the intraocular pressure twice in a row using a properly calibrated Goldmann tonometer (Carl Zeiss Meditec, Jena, Germany). The measurements should take place at the same time (± 1 hour) as preoperatively. Documentation of the average value of both measurements is required. If there is a difference of more than three mmHg between these two measurements, a third measurement is taken and the average of all three measurements is documented. The physician doctor measure the intraocular pressure and the assistant reads it. The target pressure is determined according to the criteria of WGA (World Glaucoma Association) [7]. We initially classify the patients into three groups according to visual field damage (mean deviation):

- mild damage (> -5 dB to -10 dB): target IOP ≤ 21 mmHg and IOP reduction $\geq 20\%$
- moderate damage (> -10 dB to -15 dB): target IOP ≤ 18 mmHg and IOP reduction $\geq 30\%$
- severe damage (> -15 dB): target IOP ≤ 15 mmHg and IOP reduction $\geq 40\%$

iii. *Central corneal thickness:* A corneal topography is performed using Visante OCT (Model: 1000, Carl Zeiss Meditec, Jena, Germany). We define the thinnest part of the cornea as central corneal thickness. Alternatively, if the Visante OCT topography is not available (e.g., blepharospasm), three measurements are taken by means of an ultrasonic pachymeter (OcuScan, Alcon, Fort Worth, Texas, USA) to determine the central corneal thickness. The average of these three measurements is considered central corneal thickness.

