iv. *Visual field:* The visual field examination is performed by using the Humphrey Perimeter (Humphrey Field Analyzer, Model 720i, Carl Zeiss Meditec, Jena, Germany) with threshold test centrally 24-2. The visual field is evaluated with the help of the MD value and the PSD value. The rate of progression is expressed in the form of dB / year [8]. As a significant clinical change (improvement or worsening), MD values of ≥ 3 decibels are assessed [9]. In addition, the visual field defects in the central 5-degree visual field are counted in all four quadrants (4 visual field points in total) and evaluated as follows: points with sensitivity level > 10 dB are classified with 0 point, while the points with ≤ 10 dB are evaluated with 1 point. The points are added and then divided by 4. Thus, in the evaluation, the normal regular central visual field will be rated with 0 and the advanced central scotoma in all four quadrants is rated as 1.0.

v. *Glaucoma therapy:* Number and name of the active ingredients of the prescribed topical and systemic antiglaucomatous medications preoperatively and at follow-up visits are assessed. The duration of the postoperative drug-free phase is documented. The systemic intake of acetazolamide (carbonic anhydrase inhibitor) is documented separately and evaluated as absolute failure.

vi. *Visual acuity:* First, the refraction is measured with an auto refractometer (KR-800S, Topcon, Tokyo, Japan). The best-corrected visual acuity is checked and adjusted with the best possible correction using Snellen chart. For the statistical evaluation, a visual acuity of hand motion is documented as 1/800, light perception as 1/1600, and Nulla-lux as 1/3200 [10].

vii. *The optic disc change:* Pre- and postoperative optic disc measurement is performed using the HRT II (Heidelberg Retina Tomograph II, Heidelberg Engineering GmbH, Heidelberg, Germany). The area of the optic disc and

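### Visual field worsening has no scoring rule for an eye that glaucoma has made untestable, so the worst progressors fall out of the field component of the main outcome

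*Combined protocol and SAP*

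**What the plan says.** Section 2.1 lists, among the main efficacy outcomes, "the progression of glaucoma in terms of visual field worsening and progression of glaucomatous optic disc changes".

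Section 2.4 allows two instruments before surgery, Humphrey or the Tuebingen perimeter. For the study visit it lists one: "vi. Visual field using Humphrey perimeter". Section 4.5 iv specifies the 24-2 threshold test and then states: "The visual field is evaluated with the help of the MD value and the PSD value". It adds a progression rate in dB per year, a threshold of 3 dB in MD for a significant change, and a score built from four central test points.

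Two other places deal with eyes at the bottom of the range. In 2.6, one of the criteria for complete failure is "The loss of visual acuity to 'nulla lux' because of glaucoma progression". In 4.5 vi, for the statistical evaluation, "a visual acuity of hand motion is documented as 1/800, light perception as 1/1600, and Nulla-lux as 1/3200".

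Section 5 names the software and the visit windows. Otherwise it leaves the methods to adequate procedures, with no rule for missing values.

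**The concern.** All the field measures in 4.5 iv need a test that the patient can complete. An eye without light perception cannot respond to the stimulus, so it has no MD, no dB/year rate and no 3 dB classification at that assessment. Under 2.6 the same eye is a complete failure because its glaucoma progressed. The plan can therefore record an eye as a progression failure in one outcome and have no entry for it in the field result of another.

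This loss is informative. An eye that glaucoma has made untestable is among those that lost most. If the field analysis simply uses the eyes that have an MD, both the proportion worsening by at least 3 dB and the mean dB/year will look more stable than they are. That error favours the device in a study meant to establish its long-term place.

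**Working it through.** **Sample size used.** Section 2.7 gives 21 × 8²/4² = 84, and 84/0.65 = 129.2, rounded up to 130 to invite. Both figures reproduce, and the point does not dispute them. Section 2.2 states the target as at least 84 eyes examined, so 84 is the denominator below.

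**Which outcomes hold a value for an eye at nulla lux from glaucoma**

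| Outcome | Section | Rule for this eye |
|---|---|---|
| Second success classification | 2.6 | Complete failure |
| Visual acuity | 4.5 vi | Coded 1/3200 |
| Optic disc, nerve fibre layer | 4.5 vii, viii | Own scores, which do not use the field test |
| MD, PSD, dB/year, 3 dB rule | 4.5 iv | None |
| Four-point central score | 4.5 iv | None; it needs measured sensitivities |

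The plan has devices for difficult measurements elsewhere: off-scale acuity codes, a reduced denominator for non-evaluable nerve fibre segments, and a fallback instrument for corneal thickness. The field outcome has no counterpart.

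**Size of the effect on the 3 dB proportion.** The documents give neither the share of untestable eyes nor a worsening rate, so both are assumptions.

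- s = share of the 84 eyes that are untestable, all assumed to have worsened: 3%, 5%, 10%.
- p = proportion worsening among testable eyes, which is the figure that would be reported: 10%, 20%, 30%.
- True rate = p(1 − s) + s, so the understatement is s(1 − p).
- Standard error of the reported rate = √[p(1 − p)/(84(1 − s))], treating eyes as independent.

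Example: p = 20%, s = 10%. True rate = 0.20 × 0.90 + 0.10 = 28.0%, an understatement of 8.0 points. SE = √(0.16/75.6) = 4.60 points, and 8.0/4.60 = 1.7.

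| Reported p | s | True rate | Understatement (points) | SE (points) | In SE |
|---|---|---|---|---|---|
| 10% | 3% | 12.7% | 2.7 | 3.32 | 0.8 |
| 10% | 5% | 14.5% | 4.5 | 3.36 | 1.3 |
| 10% | 10% | 19.0% | 9.0 | 3.45 | 2.6 |
| 20% | 3% | 22.4% | 2.4 | 4.43 | 0.5 |
| 20% | 5% | 24.0% | 4.0 | 4.48 | 0.9 |
| 20% | 10% | 28.0% | 8.0 | 4.60 | 1.7 |
| 30% | 3% | 32.1% | 2.1 | 5.08 | 0.4 |
| 30% | 5% | 33.5% | 3.5 | 5.13 | 0.7 |
| 30% | 10% | 37.0% | 7.0 | 5.27 | 1.3 |

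**Check with whole eyes.**

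- 2 untestable: 25/82 = 30.5% reported, (25 + 2)/84 = 32.1% with them counted.
- 4 untestable: 16/80 = 20.0% becomes (16 + 4)/84 = 23.8%.
- 8 untestable: 8/76 = 10.5% becomes (8 + 8)/84 = 19.0%.

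The direction is always the same, and the sizes agree with the table.

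**Effect on mean dB/year.** If the untestable eyes declined faster than the rest by D dB/year, the mean decline is understated by s × D, that is 0.03D to 0.10D. The documents give no basis for D, so no value is put on it.

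**The case against.** The strongest reply is that the plan excludes nobody. Section 4.5 iv is silent about untestable eyes, and section 5 would permit any sensible handling. That is correct: this is an omission, not an exclusion rule. But without an MD there is nothing to analyse, and nothing in the text returns the eye to the result, so the default outcome is its loss. An earlier postoperative field from the records might supply a rate. The plan does not say it would be used, and such a field would predate the worst of the loss.

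Several stronger readings are tempting, and the documents do not support them.

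- *A blind eye vanishes from the progression outcome, or from the study.* It does not. Section 2.1 also defines progression by disc changes, 4.5 scores the disc and nerve fibre layer separately, and 2.6 counts the eye as a complete failure. Only the field component loses it.
- *All eyes at hand motion or light perception are untestable.* Those are acuity grades. Only nulla lux makes a missing field certain. Some eyes short of that may be lost, and those are not caught by the blindness criterion in 2.6.
- *The acuity codes show that many such eyes are expected.* They are a coding convention that applies to any cause of low acuity. The documents do not show that even one such eye exists.
- *The bias arises whatever analysis is used.* A worst-rank analysis removes the eye's absence, so the choice of analysis matters. The bias also needs an eye that was testable before surgery. One that was untestable both times has no measured change to lose.
- *Eyes without a preoperative field have no target pressure.* Section 4.5 ii says "We initially classify the patients into three groups according to visual field damage (mean deviation" but does not say which examination supplies the mean deviation, so this cannot be concluded.

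It is also fair to say that the upper end of the size range is a corner case: 2.6 standard errors needs 10% untestable eyes, all worsened, against 10% observed worsening. With 3% untestable, every scenario is below one standard error.

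**Conclusion.** The point holds for the field component of the main outcome. As written, an eye that glaucoma has made untestable has no place in the 3 dB proportion or the dB/year rate, although 2.6 treats blindness from glaucoma as complete failure. The resulting bias is toward stability.

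Its size cannot be read from the documents. With 3% to 10% of 84 eyes untestable and all of them worsened, the understatement is 2.7 to 9 points at an observed 10%, 2.4 to 8 at 20%, and 2.1 to 7 at 30%, or about 0.4 to 2.6 standard errors over the whole range. With no such eyes it is zero.

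The gap is not confined to the study visit. Under 2.2, eyes with long-term data already on file contribute from the records, and they are subject to the same missing rule. Because the direction is known and the remedy is cheap, the rule should be fixed before the field data are analysed.

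**What to change.** Add to 4.5 iv:

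- An eye with a measurable preoperative field that cannot be tested at its long-term assessment (study visit or records) because of glaucomatous vision loss counts as significant worsening in the 3 dB analysis.
- In the dB/year analysis the same eye receives the worst rank, and the rate is summarised by a rank-based method.
- Eyes without an MD, or without a usable MD change, for other reasons (frailty, media opacity, no comparable preoperative field) are reported as a separate count, with the reason for each.

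The cost is a few sentences and a recode from acuity and history that are already collected. There are two downsides: someone must judge the cause of the vision loss in each such eye, and the reported progression will be slightly less favourable. This changes how outcomes are scored and has no bearing on patient care.

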the course of the rim area changes are documented and evaluated. Furthermore, the disc change is assessed and evaluated with the help of MRA (Moorfields Regression Analysis). The entire disc area is divided into 6 segments. First, the green segments lying within the standard range are rated with 0 points. The borderline yellow segments are scored 1 point and the pathologic red segments are scored with 2 points. The total number of points is added and then divided by 12. That means the normal non-glaucomatous papilla is rated with 0, the optic disc with terminal damage by glaucoma in all segments rated with 1.0.

viii. *The nerve fiber layer:* A measurement of the thickness of the peripapillary nerve fiber layer is carried out by the Stratus OCT (Model 3000, Carl Zeiss Meditec, Jena, Germany). The evaluation of nerve fibers is performed according to the number of damaged segments and the extent of damage of each segment. Each measurement results in 12 segments. The healthy segments (shown in green) are classified with 0 points, the moderately damaged segments (shown in yellow) are classified with 1 point and the markedly damaged segments in red are classified with 2 points. The total number of points is added and divided by 12, resulting in an average number of evaluable segments. The numbers of non-evaluable segments (shown in white), if any, are subtracted from the 12 segments and the total score is then divided by the number of segments that can be evaluated.

ix. *Description of the CyPass stent and the bleb:* By using the Visante OCT (Model: 1000, Carl Zeiss Meditec, Jena, Germany) the stent and the stent-associated bleb are morphologically visualized. It is assessed if the stent lumen is clear or if there is a CyPass occlusion. The size of the bleb is assessed and classified morphologically into 4 groups. While the largest bleb is assessed with 3 points, the absence of the bleb is rated with 0 points.

x. *Position of the stent:* The stent position is assessed by a gonioscopic examination of the angle of the anterior chamber with the Goldmann goniolens. Possible iris tissue growing and anomalies of the neighboring tissue (goniosynechiae) are documented as follows:

- If there are no synechiae, it is classified with 0 points.
- Goniosynechiae around the stent but without collar or lumen involvement are classified with 1 point.
- Collar and / or lumen involvement of goniosynechiae is classified as 2 points.

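### The nerve fibre layer is evaluated only by a three-colour score with a ceiling at red; no analysis of change in the measured thickness is specified

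*Combined protocol and SAP*

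**What the plan says.** Section 2.4 lists the measurement at both time points: among the preoperative findings, "Retinal nerve fiber layer thickness measured with Stratus OCT", and among the study-visit examinations, "Nerve fiber thickness measured with Stratus OCT". Section 4.5 viii confirms the device: "A measurement of the thickness of the peripapillary nerve fiber layer is carried out by the Stratus OCT".

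Section 4.5 viii then sets the evaluation: "The evaluation of nerve fibers is performed according to the number of damaged segments and the extent of damage of each segment". The scale is built as follows.

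- Segments: "Each measurement results in 12 segments".
- Points: green scores 0, yellow scores 1, and "the markedly damaged segments in red are classified with 2 points".
- Aggregation: "The total number of points is added and divided by 12, resulting in an average number of evaluable segments". Segments shown in white are taken out of the denominator.

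No other evaluation of the nerve fibre layer is described. Section 5 names the software and leaves the choice of statistical procedures open, so it does not supply an analysis of thickness.

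Two comparisons within the plan matter. Section 4.5 iv keeps MD, PSD and a rate in dB per year for the visual field, beside its central point score. Section 4.5 vii keeps rim area for the disc, beside its colour score. Section 2.1 defines progression in the main outcome by visual field and optic disc change, and does not name the nerve fibre layer there or among the secondary outcomes.

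**The concern.** Thickness is a continuous quantity, listed for both time points on the same named device. The plan describes turning it into three grades and says nothing of analysing the thickness itself. This has two consequences for measuring change.

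First, the scale has a ceiling. A red segment already has the highest grade, so its score cannot rise whatever further loss occurs. The more red segments an eye has before surgery, the less progression its score can show.

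Second, the scale is coarse below the ceiling. Thinning that stays within the green or yellow band scores nothing, while a small loss that crosses a boundary scores a full point.

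What is at stake is the reading of the RNFL result. A small mean change in score could reflect little loss, loss within bands, or loss in segments already at the top grade. The score alone cannot separate these.

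**Working it through.** The plan gives no RNFL figure to reproduce: no expected change, SD, colour cut-offs or baseline distribution. The sample size in section 2.7 does not rest on this measure. The check is therefore arithmetic on the scale as defined.

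**Inputs (section 4.5 viii).** 12 segments; 0, 1 or 2 points each; total divided by 12 when all segments are evaluable.

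**Range.** Minimum 0/12 = 0. Maximum (12 × 2)/12 = 24/12 = 2.0.

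**Room to rise.** With r red, y yellow and the remaining segments green:

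- score = (2r + y)/12
- largest possible rise = 2 − score
- share of segments that cannot register further loss = r/12

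| Red segments | Share at ceiling | Score, rest green | Largest rise, rest green | Score, rest yellow | Largest rise, rest yellow |
|---|---|---|---|---|---|
| 3 | 25% | 0.50 | 1.50 | 1.25 | 0.75 |
| 6 | 50% | 1.00 | 1.00 | 1.50 | 0.50 |
| 9 | 75% | 1.50 | 0.50 | 1.75 | 0.25 |
| 12 | 100% | 2.00 | 0 | 2.00 | 0 |

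**Worked eye (assumed).** With 8 red and 4 yellow: (8 × 2 + 4 × 1)/12 = 20/12 = 1.67. The largest rise is 2.00 − 1.67 = 0.33, and 8 of 12 segments cannot register loss.

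**Loss within a band (assumed cut-offs).** Take red as below 60, 70 or 80 µm, and yellow as the next 10 µm above. Apply losses of 5, 10 and 15 µm to a single segment.

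- Starting at 55 or 45 µm (red under all three sets): change in score 0 in every case.
- Starting at 110 µm (green under all three sets): change in score 0 in every case.
- Starting at 90 µm with red below 80: a loss of 5 µm scores 1 point, and a loss of 15 µm scores 2.

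The same 15 µm loss therefore scores 0 or 2 depending on where the segment started. The cut-offs are invented for illustration. That red is a ceiling, and that loss within a band scores zero, does not depend on them.

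**The case against.** The strongest reply is that the consequences are limited, and most of it stands.

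*Main outcome.* A reader might infer that the study's progression result is masked in the most damaged eyes. The documents do not support that. Section 2.1 defines progression by visual field and disc, and an eye with all 12 RNFL segments red is still assessed by MD, PSD, dB per year and rim area. One qualification is that section 2.4 allows preoperative fields from either the Humphrey or the Tübingen perimeter, against Humphrey alone at the study visit. Some field comparisons may therefore mix instruments, whereas HRT II and Stratus are each named at both times. That makes RNFL thickness worth analysing, but does not make it part of the main outcome.

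*Discarded data.* A reader might infer that the thickness values are thrown away. Nothing says so. They are listed for collection, and the data collection form (Appendix 1) is not in the available text. What can be said is that no analysis of them is specified, which is partly an instance of the general openness of section 5.

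*Size.* A reader might assume that many segments are red before surgery because section 4.5 ii has a severe band. That band serves to set target pressure and predicts no frequencies. A claim of lost power would also go too far, since no RNFL test is planned.

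*Stability.* Section 4.5 viii sets no rule that an unchanged score means a stable eye. The risk lies in interpretation.

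None of this removes the ceiling or supplies an analysis of thickness.

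**Conclusion.** The point holds as a limitation of one supporting measure. As described, the RNFL evaluation cannot register further thinning of red segments or thinning within a colour band. Of the field, disc and nerve fibre layer assessments, it alone has no continuous evaluation described.

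The size for a given eye is exact once its segment colours are known: each red segment contributes no possible rise, and an eye at 2.0 has none at all. The size for the study is unknown, because the number of eyes near the ceiling is not given and cannot be derived from the documents. The 8-red and 12-red eyes are assumptions for illustration.

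This is an inexpensive improvement to the RNFL analysis. It does not challenge the main progression outcome.

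**What to change.** In section 4.5 viii:

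1. Make the within-eye change from before surgery to the study visit in average RNFL thickness (µm), with a 95% CI, the RNFL progression measure. Add the 12 segments where the baseline record holds them. The interval should allow for patients who contribute both eyes, which section 2.2 permits.
2. Keep the colour score as a description at each visit.
3. Report how many eyes and how many segments were at the maximum score at baseline.
4. Report the number of eyes with paired thickness values.

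Do not repair the colour score by restricting its change to segments that were not red at baseline. That selects on the baseline value: it drops segments that could only stay the same or improve and keeps those that can worsen, so measurement noise alone would push the result towards apparent worsening.

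Naming thickness change as the RNFL progression measure need not alter the outcomes in section 2.1; it can remain supporting evidence.

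The cost is transcription of thickness values, with no new examination. The preoperative part comes from medical records, so some average or segment values may be missing; item 4 makes that visible.

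### The nerve fibre layer score is averaged over the segments readable at each visit, so a pre/post comparison can mix real change with a change in which segments were readable

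*Combined protocol and SAP*

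**What the plan says.** Section 4.5 viii of the combined protocol and SAP defines a colour score for the Stratus OCT measurement. "Each measurement results in 12 segments". Green counts 0 points, yellow counts 1 and red counts 2; on the worst grade the wording is "the markedly damaged segments in red are classified with 2 points". The base rule is "The total number of points is added and divided by 12, resulting in an average number of evaluable segments". For white segments it is changed: "The numbers of non-evaluable segments (shown in white), if any, are subtracted from the 12 segments"; points are then averaged over what is left. The denominator is thus set separately for each measurement.

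Section 2.4 lists the measurement twice. Before surgery it is taken from the medical record ("Retinal nerve fiber layer thickness measured with Stratus OCT"), and the same device is used again at the study visit. The inclusion criteria put that visit 3 to 8 years after implantation.

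Section 2.1 counts glaucoma progression within the main research outcome, and describes it through visual field worsening and "progression of glaucomatous optic disc changes". The nerve fibre layer is not named there.

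No section says how the two nerve fibre layer scores are to be compared, whether segments are matched between visits, or how few readable segments are acceptable. Section 5 leaves the choice of statistical method open.

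**The concern.** Averaging over the readable segments is reasonable for describing one scan. The difficulty comes when two such averages are compared. A segment that is white at one visit only enters one average and not the other, so the two scores describe different parts of the same eye. If the unmatched segments are more damaged than the rest, losing them at follow-up makes the eye look better. If they are healthier, losing them makes it look worse. Either can happen with no change in any segment.

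At stake is the reading of structural change over several years. The score supports the progression question, and its scale is coarse: a real one-grade step in one of 12 segments moves it by only 1/12 = 0.083. An artefact of that size or larger could hide such a step or imitate one.

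**Working it through.** The plan gives no numerical result for this score, so there is no figure to reproduce. The check applies the rule of section 4.5 viii to an eye in which no segment changes grade.

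**Inputs from section 4.5 viii:** 12 segments; green 0, yellow 1, red 2; score = sum of points / number of evaluable segments.

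**Assumed, because the documents do not give them:** the grade profile of the eye, and how many segments are white (1 to 4, at follow-up only).

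**Formula.** Let M be the mean grade over all 12 segments. Let k segments with mean grade w be white at follow-up. The apparent change is

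(12M − kw)/(12 − k) − M = k(M − w)/(12 − k).

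It is zero when w = M, that is, when the lost segments have the same mean grade as the rest.

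**Eye A: 2 red, 10 green, unchanged.** Preoperative score 4/12 = 0.33.

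| White at follow-up | Follow-up score | Apparent change | Pairs out of 66 |
|---|---|---|---|
| both red | 0/10 = 0.00 | −0.33 | 1 |
| one red, one green | 2/10 = 0.20 | −0.13 | 20 |
| two green | 4/10 = 0.40 | +0.07 | 45 |

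If the two white segments are a random pair:
- Mean change = [1(−0.333) + 20(−0.133) + 45(0.067)]/66 = 0.
- Variance = [0.111 + 0.356 + 0.200]/66 = 0.0101, so the SD is about 0.10.
- The extreme case has probability 1/66 = 1.5%.

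A case with no artefact: if 1 red and 5 green segments are white, the score is 2/6 = 0.33, the same as 4/12.

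**Eye B: 3 red, 3 yellow, 6 green, unchanged.** Preoperative score 9/12 = 0.75. Range of apparent change over all possible sets of white segments:

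| White segments | Lowest | Highest |
|---|---|---|
| 1 | −0.11 | +0.07 |
| 2 | −0.25 | +0.15 |
| 3 | −0.42 | +0.25 |
| 4 | −0.50 | +0.38 |

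With two white, the lowest value is 5/10 − 0.75 (two red lost) and the highest is 9/10 − 0.75 (two green lost). The SD over random pairs is 0.11, with mean zero. The lowest value is three times a real one-grade step (0.25/0.083).

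**Other profiles, two white.** A mild eye (1 red, 2 yellow, 9 green; 4/12 = 0.33) ranges from −0.23 to +0.07. A severe eye (6 red, 3 yellow, 3 green; 15/12 = 1.25) ranges from −0.15 to +0.25. An eye with one uniform grade gives zero.

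**Real worsening hidden.** Take eye A. At follow-up both red segments are white and two green ones have become yellow. The plan's score goes from 0.33 to 2/10 = 0.20, an apparent improvement of 0.13. On the 10 segments readable at both visits it goes from 0/10 = 0.00 to 2/10 = 0.20, a worsening.

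**Common segments.** For an unchanged eye, scoring both visits on the same segments gives a change of exactly zero for any white pattern. For eye B with two red white, it is 5/10 against 5/10.

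**Dividing by 12 throughout is no remedy.** It counts white segments as healthy: eye B with two red white would score 5/12 = 0.42 against 0.75.

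**The case against.** The strongest reply is that the plan does not state the comparison being criticised. Section 4.5 vii speaks of disc measurements before and after surgery and of the course of rim area change; section 4.5 viii only says how to score one measurement. Matching by segment is left open, not ruled out. This stands as a limit: the pre/post comparison is inferred from collection of the same measurement at both times. It is the evident use, and nothing in the text would lead an analyst to match segments.

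A reader might infer that the main efficacy outcome is affected. The documents do not support that. Section 2.1 names visual field and optic disc, and the disc is assessed under a separate item on another device (HRT II). The nerve fibre layer is supporting structural evidence.

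A reader might also infer that every eye whose readable segments differ between visits gets a wrong change score. That is false, as the 2/6 = 4/12 case shows.

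Finally, one might infer a systematic shift. The mean artefact is zero if segments are white at random, and the full false recovery in eye A is then a 1.5% event among random pairs. Bias needs white status to be related to damage, which no section states. Lens condition is recorded at both times, but the documents do not link it to unreadable segments.

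The remedy is not neutral either. If damaged segments are the ones that become unreadable, common-segment scoring does not see the loss in them. This stands, and is a reason to keep the per-visit score alongside.

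**Conclusion.** The point holds as a cheap improvement to a supporting measure. Under the stated rule, comparing an eye's two scores can show change where there is none, or hide change where there is some, whenever the segments readable at only one visit differ in mean grade from the rest. With two white segments at one visit, the false change in the profiles examined runs from −0.33 to +0.25, against 0.083 for a real one-grade step in one segment. For a random pair the mean is zero and the SD is about 0.10 to 0.11 in eyes A and B, which is noise; it becomes bias only if white status is related to damage.

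These figures rest on assumed grade profiles and assumed numbers of white segments. The documents give no frequency of white segments, so the effect on the study's results is unknown and could be small.

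**What to change.** Add to section 4.5 viii: for the comparison of preoperative and study-visit measurements, both scores of an eye are calculated from the segments evaluable at both visits only, and the number of common segments is reported for each eye. Keep the present per-visit score for cross-sectional description, and repeat the comparison with it as a sensitivity analysis. If the two comparisons differ, the change in readable segments matters and should be discussed.

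The cost is one sentence, a changed spreadsheet formula, and some data work. The present score needs only a count of each colour; the common-segment score needs the colour by segment position at both visits. If the preoperative records were extracted as totals, the old printouts may have to be read again. Loss in segments not readable at both visits is not counted, and the report should say so.
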